11.1.2 Documenting Adverse Events

It is the responsibility of the Investigator to document in the eCRF all AEs/SAEs that occur during the course of the study. AEs/SAEs should be collected after the informed consent form is signed and usually at the Screening visit. The AEs/SAEs should be documented as a single medical diagnosis. When this is not possible, the AE/SAEs should be documented in terms of signs and/or symptoms observed by the Investigator or reported by the subject at each study visit.

All AEs/SAEs occurring after the subject signs the informed consent through the last study visit must be reported, regardless of whether or not the AEs/SAEs are considered drug-related. All AEs/SAEs, whether in response to a query, observed by the study site personnel, or reported spontaneously by the subject, will be recorded.

At each visit during the study, the subject will be assessed for the occurrence of new and ongoing AEs. Dermal safety and tolerability that result in the subject requiring a concomitant therapy or discontinuation from the study will be reported as an AE/SAE. The following data will be collected on all AEs and recorded on the appropriate eCRF:

- Event name (diagnosis preferred, if unknown, record the signs/symptoms)

- Onset date and end date
- Maximum severity
- Seriousness
- Action taken regarding IP
- Corrective treatment, if given
- Outcome

In addition, the Investigator's assessment of causality will be recorded

It is not necessary to capture multiple occurrences of an AE separately if the event recurs at short intervals. In such instances the end date of the AE is the date when the event resolved last and did not recur. If however the event recurs after long intervals, then the subsequent event may be captured as a separate event. The PI may use his discretion to determine what constitutes a long or short interval between events and which event is reported once versus more than once. Furthermore, protocol defined end points (e.g new BCCs on the face, nSEBs on the face and BCC surgeries on the face) will be summarized as efficacy parameters and are not to be reported as AEs/SAEs.

In the clinical database, all AEs including SAEs are to be followed for a minimum up to the 30 day follow up visit. In the source documents, any and all AEs including SAEs must be thoroughly documented to conclusion or in the opinion of the investigator, the event has resolved or stabilized.

11.1.3 Serious Adverse Events

All AEs will be assessed as either serious or non-serious.

An SAE or serious adverse reaction is defined as any untoward medical occurrence that at any dose:

- Results in death
- Is immediately life threatening, (the term "life threatening" in the definition of "serious" refers to an event in which the subject is at risk of death at the time of the event; it does not refer to an event which hypothetically might have caused death if it were more severe)
- Requires in-patient hospitalization or prolongation of existing hospitalization (hospitalization for elective surgery for a condition present at Screening is not considered an AE)
- Results in persistent or significant disability/incapacity (permanent or substantial disruption of a person's ability to conduct normal life functions)
- Is a congenital anomaly/birth defect

- Is a medically important event that may not be immediately life threatening or result in death or hospitalization, but may jeopardize the subject and may require medical or surgical intervention to prevent any of the above listed outcomes

If the BCC surgery requires as per standard of care, that the patient be hospitalized, then this hospitalization is not an SAE.

Note: A spontaneous abortion will be considered an SAE and must be reported per Reporting of SAEs under Section 11.1.6. Pregnancy in and of itself is not an SAE, but a subject who becomes pregnant must discontinue IP application immediately and the pregnancy will be followed to term (and ideally the child will be followed afterward if the subject consents) or termination. Any birth defect or other serious issue that may arise during the pregnancy or due to fetal exposure will be considered an SAE.

11.1.4 Assessment of Severity

The severity assigned to an AE should be determined by the maximum severity of the AE.

The categories described below should be used to estimate the severity of AEs:

- **Mild:** Transient or mild discomfort; no limitation in activity; no medical intervention/therapy required
- **Moderate:** Mild to moderate limitation in activity; some assistance may be needed; no or minimal medical intervention/therapy required
- **Severe:** Marked limitation in activity; some assistance usually required; medical intervention/therapy required; hospitalization or prolongation of current hospitalization possible; may be incapacitating or life threatening

11.1.5 Assessment of Causality

The Investigator should assess the relationship of the AE, if any, to the IP. The following should be taken into account when assessing SAE causality:

- Positive temporal relationship to IP, such as if the IP was discontinued and the SAE resolved or the event recurred after re-introduction.
- If there is a reasonable possibility that the AE is associated with an underlying or concomitant illness.
- Possible association with previous or concomitant therapy.
- No temporal relationship to the IP and/or a more likely alternative etiology exists.
- If the AE is directly related to study procedures or a lack of efficacy.

The following classifications should be used when evaluating the relationship of AEs and SAEs to the investigational drug.

1. **Not Related:** No relationship between the experience and the administration of IP; related to other etiologies such as concomitant medications or subject's clinical state.
2. **Unlikely:** The current state of knowledge indicates that a relationship is unlikely.

3. **Possibly:** A reaction that follows a plausible temporal sequence from administration of the IP and follows a known response pattern to the suspected IP. The reaction might have been produced by the subject's clinical state or other modes of therapy administered to the subject.
4. **Probably:** A reaction that follows a plausible temporal sequence from administration of the IP and follows a known response pattern to the suspected IP. The reaction cannot be reasonably explained by the known characteristics of the subject's clinical state or other modes of therapy administered to the subject.
5. **Definitely:** A reaction that follows a plausible temporal sequence from administration of the IP and follows a known response pattern to the suspected IP and can be confirmed with a positive re-challenge test or supporting laboratory data.

11.1.6 Reporting of Serious Adverse Events

SAEs will be captured in both the clinical and safety database.

All SAEs, regardless of cause or relationship, that occurs after the subject first consents to participate in the study (i.e., signs the informed consent) and throughout the duration of the study and for 30 days following the last IP application will be captured in the clinical database via the eCRFs (Section 11.1.2).

SAEs also will be captured in the safety database. An initial SAE Report must be completed for all SAEs (irrespective of relatedness) with an onset date within 30 days from the date of last IP application. An initial SAE Report must also be completed for Related SAEs (possibly, probably or definitely) regardless of the time elapsed from the last dose (even if the study has been closed).

When new, significant information for an SAE is obtained, as well as when the outcome of an SAE is known, the Investigator must submit a Follow-Up Report. If the subject was hospitalized, a copy of the discharge summary must be included as part of the subject's medical file. For related events, the Investigator should monitor the subject until the outcome of the SAE is known. This may require periodic Follow-Up Reports.

PellePharm and the study CRO must be notified of all SAEs (regardless of causal relationship to IP) within 24 hours of the Investigator's knowledge of the event by faxing or emailing a completed SAE report to the CRO Medical Monitor.

If there are serious, unexpected AEs associated with the use of the IP, PellePharm (or designee) will notify the appropriate regulatory agency(ies) and all appropriate parties as appropriate (e.g., IRB) on an expedited basis. It is the responsibility of the Investigator to promptly notify the IRB/IEC of all unexpected SAEs involving risk to human subjects.

11.1.7 Emergency Contact

In the event of a medical emergency (i.e., an event that requires immediate attention regarding the treatment of a subject, operation of the clinical study, and/or the use of

investigational drug), investigational site personnel should endeavor to contact the Medical Monitor to discuss the situation.

11.1.8 Expedited Serious Adverse Event Reports

An AE, whether serious or non-serious, is designated unexpected if it is not reported in the reference safety section of the IB or if the event is of greater frequency, specificity or severity than so reported.

PellePharm will notify regulatory authorities of unexpected related SAEs and all participating study sites in writing for submission by the Investigator to the IRB/IEC. This notification will be in the form of a Safety Update to the IB (i.e., “15-day letter”).

Upon receiving such notices, the Investigator must review and retain the notice with the IB and immediately submit a copy of this information to the responsible IRB/IEC, according to local regulations. The Investigator and IRB/IEC will determine if the informed consent requires revision. The Investigator should also comply with the IRB/IEC procedures for reporting any other safety information.

12 STATISTICS

All statistical processing will be performed using SAS® unless otherwise stated. For categorical parameters, the number and percentage of subjects in each category will be presented. For continuous parameters, descriptive statistics will include n (number of subjects), mean, standard deviation (SD), median, minimum, and maximum.

The multiple imputation (MI) method will be the primary method for dealing with missing data. Last Observation Carried Forward (LOCF) and observed case analyses will be done as sensitivity analyses.

A statistical analysis plan (SAP), describing all statistical analyses will be provided as a separate document. The SAP will be finalized prior to unblinding of the study treatments.

12.1 Analysis Population

The primary population for efficacy analyses will be the Intent-to-Treat (ITT) population, defined as all subjects who were randomized. Subjects will be assigned to treatment groups as randomized. The per-protocol (PP) population will be used for supportive efficacy analyses. Subjects will be assigned to treatment groups as treated (not as randomized). The Safety population will consist of all subject who have applied IP at least once.

12.2 Subject Disposition

A tabulation of subject disposition will be provided. The tabulation will include the numbers of subjects who enter the study, complete the study, and discontinue the study. The reasons for discontinuation will be included.

12.3 Demographics and Baseline Characteristics

Subject demographic data and Baseline characteristics will be summarized by treatment group using descriptive statistics for the ITT population.

12.4 Protocol Deviations

All PDs will be reported to PellePharm and recorded throughout the study. A tabulation of PDs will be included in the final study report.

12.5 Compliance

Compliance will be tracked throughout the study. Results of compliance assessments (weight of returned drug, etc.) will be tabulated, and descriptive statistics will be used to compare the 2 groups. For the per protocol population, a sensitivity analysis will be conducted based on compliance.

12.6 Assessment of Efficacy

12.6.1 Efficacy Summaries

The efficacy endpoints are intended to compare twice daily application of Patidegib Topical Gel, 2%, and Vehicle. Efficacy assessments will be summarized descriptively by treatment group and visit.

12.6.1.1 Primary Endpoint

The primary endpoint is the number of new BCCs per subject by Month 12.

12.6.1.2 Secondary Endpoints

The secondary efficacy endpoints are:

1. The number of nSEBs per subject by Month 12.
2. The proportion of subjects developing ≥ 2 facial new BCCs by Month 12.
3. The proportion of subjects developing ≥ 1 facial new BCCs by Month 12.
4. The number of new BCCs per subject by Month 9.
5. The number of new BCCs per subject by Month 6.
6. aBCCdex change in Lesion Symptoms scale score from Baseline to Month 12.

An nSEB is a histologically verified BCC that was surgically removed because of possible functional facial/health impairment as determined by the Investigator.

Also, nSEBs are facial BCCs with a longest diameter of [REDACTED] that:

- a. were not surgically eligible BCCs (SEBs) at Baseline,
- b. have grown by [REDACTED] in longest diameter from Baseline, and
- c. have been verified histologically.

12.6.1.3 Exploratory Endpoints

The exploratory endpoints are:

1. The proportion of SEBs that undergo clinical resolution at Month 12.
2. The number of BCC surgeries from Baseline to Month 12.
3. Change in aBCCdex Worry About Future Lesions scale score from Baseline to Month 12.
4. Change in aBCCdex Mental Health scale score from Baseline to Month 12.
5. Change in aBCCdex Social/Relationships scale score from Baseline to Month 12.
6. Change in aBCCdex Life Impact scale score from Baseline to Month 12.

12.6.2 Efficacy Analyses

The primary endpoint is the number of new BCCs per subject that develop from baseline to Month 12. The number of new BCCs that develop from Baseline to Month 12 will be analyzed using a negative binomial regression to compare treatment groups with number of BCCs at Baseline, Age [REDACTED], gender, prior HHI therapy, and geographic region strata (North America, Europe) as covariates. PROC GENMOD of SAS will be used with distribution=Negbin.

In order to assess the impact of parametric assumptions, a non-parametric rank analysis of covariance (ANCOVA, Stokes et al) will be provided as a sensitivity analysis with number of BCCs at Baseline, prior HHI therapy, gender, age [REDACTED], and geographic region as covariates.

The Negative Binomial regression was selected as the primary method of analysis to account for the potential for overdispersion. Using the Negative Binomial model, the power will be somewhat higher than the one calculated using a non-parametric Wilcoxon-Mann-Whitney test. The proposed sensitivity analysis, Rank ANCOVA, was selected to corroborate the results from the Negative Binomial model. If the distribution is markedly different from Negative Binomial (and unknown to sufficiently allow a different parametric regression model), then the non-parametric ANCOVA gives type-1 error closer to the nominal level.

The number of nSEBs that develop from Baseline to Month 12 will be analyzed using a Negative Binomial regression to compare treatment groups with number of BCCs at Baseline, Age [REDACTED], gender, prior HHI therapy, and geographic region as covariates. Secondary endpoints that are based on number of new BCCs will be analyzed similar to the primary endpoint. The proportion of subjects with at least two new BCCs lesions and the proportion of subjects with at least one new BCC lesion will be analyzed using a logistic regression to compare treatment groups with number of BCCs at Baseline, Age [REDACTED], Gender, and prior HHI therapy and geographic region as covariates. Change in aBCCdex will be analyzed using an ANCOVA model with treatment group as a main effect, Baseline aBCCdex, prior HHI therapy, gender, age strata, and geographic region as covariates. Testing of secondary endpoints will be done sequentially at a two-sided 0.05 level.

The primary method for dealing with missing data will be the MI method discussed in detail in Section 12.7.6.

LOCF and observed case analyses will be done as sensitivity analyses.

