6.1.2 Stratification Parameters

The study design incorporates stratification to ensure that potential Baseline confounders of efficacy are distributed evenly across treatment arms. The assignment of subjects into the study is being stratified based on Gender, Age and previous HHI therapy.

Gender is a potential confounder as female subjects had more tumor response compared with male subjects in the prior Pelle-926-202 Phase 2 study. However, both females and male subjects treated with active treatment had fewer nSEBs compared with subjects treated with vehicle.

Female subjects may have higher topical compliance as seen in other topical trials.⁹ Gender will be used as a stratification factor in this Phase 3 trial.

Previous HHI therapy might also confound the assessment of efficacy. In the trial of oral vismodegib for subjects with Gorlin Syndrome, the rate of development of nSEBs was lower after vismodegib was discontinued (██████████) than it had been during placebo treatment prior to vismodegib treatment (██████████).⁸ It is also likely that it is the subjects with more severe disease that are prescribed oral HHIs. For these reasons, previous HHI therapy is a stratification parameter.

Advanced age has been found to correlate with higher numbers of BCCs and new tumors in Gorlin Syndrome subjects from a natural history study.¹⁰ Age is therefore a stratification factor to avoid confounding age-related rates of Baseline tumor progression across treatment groups.

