12.7.6 Handling of Missing Data

The primary method for dealing with missing data will be the MI method. The MI model will be detailed in the SAP. One hundred imputations will be generated using PROC MI of SAS. Fully Conditional Specification (FCS) model will be used with either new BCCs or nSEBs at prior post-Baseline visits, treatment group, number of BCCs at Baseline, prior HHI therapy, gender, age strata, and geographic region as covariates to impute the data. The seed to be used is 20180330. The results of the 100 analyses will be transformed into a normal statistic and combined into a single analysis using PROC MIANALYZE.

LOCF and observed case analyses will be done as sensitivity analyses.

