2.2 Sample Size Determination

In the UK Phase 2 study of patients with Gorlin syndrome (Pelle-926-201), the mean number of nSEBs (erroneously stated in the protocol as mean number of new BCCs in the Section on Sample size determinations) at 6 months was █ in the Patidegib Topical Gel, 2%, group with an SD of █, and a mean of 1.4 in the Vehicle Gel group with a SD of 1.52. The effect size was 0.81. Because the current trial is longer, more conservative assumptions are made. It is assumed that at 6 months, the mean number of nSEBs in the Patidegib Topical Gel, 2%, group will be 0.6, with an SD of █, while at 6 months the mean and SD in the Vehicle Gel group will be the same as in the Phase 2 study at 6 months for an effect size of 0.63. At 12 months, it is assumed that the means and SDs will be twice those of 6 months. With these assumptions, █ subjects in the Patidegib Topical Gel, 2%, group and 63 in the Vehicle Gel group (for a total of █ subjects) will give >90% power for a 2-sided 0.05 level statistical significance. To account for a 16% drop-out rate, approximately 150 subjects will be randomized.

The primary endpoint of number of qualifying nSEBs per subject by Month 12 may be affected by follow-up time. Based on the UK Phase 2 study (Pelle-926-201), it is projected that the power calculated above will be substantially similar unless marked differences are seen between the treatment arms in follow-up time. Sample size was calculated based on a Wilcoxon-Mann-Whitney test which is conservative if the underlying distribution is Negative Binomial.

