Variables requiring calculation will be derived using the following formulas:

Days – A duration expressed in days between 1 date (date1) and another later date (date2) is calculated using the formulas noted below:

$$\text{duration in days} = \text{date2} - \text{date1} + 1$$

Months – A duration expressed in months is calculated using the INTCK function of SAS as follows:
months=intck('month','date1'd,date2'd, 'continuous').

Pelle-926-301 Statistical Analysis Plan

17 June 2020

Years – A duration expressed in years between 1 date (date1) and another later date (date2) is calculated as follows:

duration in years = intck('year',date1'd,date2'd, 'continuous').

Age – Age is calculated as the number of years from the date of birth (DOB) to the date of informed consent (DOIC). If the month of DOIC < month of DOB or the month of DOIC=DOB and the day of DOIC < day of DOB, then the following formula is used:

age (years) = year of DOIC – year of DOB – 1.

Otherwise, the following formula is used:

age (years) = year of DOIC – year of DOB.

Height – Height entries made in inches (in) are converted to centimeters (cm) using the following formula:

height (cm) = height (in) × 2.54.

Weight – Weight entries made in pounds (lb) are converted to kilograms (kg) using the following formula:

weight (kg) = weight (lb)/2.2046.

Body Mass Index (BMI) – BMI is calculated using height (cm) and weight (kg) using the following formula:

BMI (kg/m²) = weight (kg)/[[height (cm)/100]²].

Temperature – Temperature entries in degrees Fahrenheit are converted to degrees centigrade using the following formula:

temp (degrees centigrade) = 5/9 × [temp (degrees Fahrenheit) – 32].

Change from baseline – Change from baseline will be calculated as:

Change = postbaseline value – baseline value.

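### Age appears to enter the lesion-count models only as the randomisation stratum; adding age in years beside it would give a small, nearly free gain in precision

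*Protocol*

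**What the plan says.** **Where the coding is explicit.** Protocol 12.6.2 lists for the change in aBCCdex "Baseline aBCCdex, prior HHI therapy, gender, age strata, and geographic region as covariates". Protocol 12.7.6 lists for the multiple imputation "prior HHI therapy, gender, age strata, and geographic region as covariates to impute the data".

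**Where it is inferred.** The primary negative binomial model in protocol 12.6.2 names the baseline BCC count, then age with its coding blacked out, then "gender, prior HHI therapy, and geographic region strata (North America, Europe) as covariates". The nSEB and logistic models there, and the models in SAP 2.5.1, 2.5.2 and 3.2, have the same gap. Remnants such as a closing reference to years or years old (protocol synopsis; SAP 2.5.1 and 2.5.2) read like a cut-point. SAP 3.3 groups age with the stratification factors. No visible text enters age as a continuous term. The blacked-out text is not a fault of the plan, but it limits what can be asserted.

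**Why age matters.** Protocol 6.1.2 states: "Advanced age has been found to correlate with higher numbers of BCCs and new tumors in Gorlin Syndrome subjects".

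**What is held.** Protocol 8.1.4 records date or year of birth where local rules allow. SAP Appendix D derives age in whole years at informed consent.

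**The concern.** The primary endpoint is a count of new BCCs, and the protocol's own reason for stratifying on age is that age goes with new tumours. A stratum treats everyone on the same side of the cut as alike. Any remaining age gradient within the stratum goes into the dispersion parameter and slightly widens the interval for the rate ratio. The imputation model for the counts likewise loses part of a predictor that is already in the database.

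Only precision is at stake. It has some value here because the trial was sized on nSEBs, and protocol 12.8 concedes that power for new BCCs may differ.

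**Working it through.** **1. The plan's own figure.** SAP 2.2 gives for vehicle at 6 months "a mean of 1.4 in the Vehicle Gel group with a SD of 1.52" and for patidegib "group will be 0.6, with an SD of" a value that is blacked out there; the protocol synopsis gives 0.94.

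- Pooled SD = √((0.94² + 1.52²)/2) = 1.264.
- Effect size = (1.4 − 0.6)/1.264 = 0.633; the SAP states 0.63.
- Power with 63 per arm, two-sided 0.05: 94.4% by the normal approximation; 93.5% for a Wilcoxon test with relative efficiency 3/π; 91.0% at the worst-case efficiency of 0.864.
- Simulated Wilcoxon tests on negative binomial counts: 94.3% with the 6-month inputs and 97.2% with the 12-month inputs.
- 126/(1 − 0.16) = 150 randomised.

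The statement that the design "will give >90% power for a 2-sided 0.05 level statistical significance" therefore reproduces. It rests on an unadjusted test, so the coding of age does not enter it.

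**2. Linear approximation.** Let R² be the share of residual variance that age explains beyond the other covariates. A two-level cut of a normal variable keeps a fraction c of this: c = 2/π = 0.637 for a median cut and 0.539 for a 25/75 cut. Variance with the stratum relative to variance with age in years is (1 − cR²)/(1 − R²).

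| R² (assumed) | Ratio, median cut | Equivalent subjects, 126 × (ratio − 1) |
|---|---|---|
| 0.02 | 1.007 | 1 |
| 0.05 | 1.019 | 2 |
| 0.10 | 1.040 | 5 |
| 0.15 | 1.064 | 8 |

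For a 25/75 cut at R² = 0.15 the ratio is 1.081, or about 10 subjects. Across all these settings the power gain is 0 to 1.3 points.

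**3. Count scale, by hand.** Assume an age SD of 14 years, a median cut, dispersion 1.0, and the 12-month planning means of 1.2 and 2.8 (twice the 6-month values).

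- Averaged over arms, each subject contributes (1/1.2 + 1/2.8)/2 + 1.0 = 1.595 to the variance of the log rate ratio.
- At a rate ratio of 1.2 per decade, the log-rate variance due to age is (1.4 × ln 1.2)² = 0.0652. The part left within the two halves is 0.0652 × (1 − 0.637) = 0.0237.
- Share removable by age in years: 0.0237/(1.595 + 0.0237) = 1.5%.
- The same steps give 0.0490 and 3.0% at 1.3 per decade, and 0.1171 and 6.8% at 1.5.

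Correlation of age with the baseline count lowers these shares; a smaller dispersion raises them.

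**4. Simulation.** Negative binomial regression was fitted to the same simulated data with and without age in years beside a two-level stratum. There were 126 subjects, and a baseline count correlated 0.4 with age was in both models.

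| Age effect per decade (assumed) | Change in model variance of log rate ratio |
|---|---|
| none | about +0.4% |
| 1.2 | about −1% |
| 1.3 | about −3% |
| 1.5 | about −8% |

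Type I error stayed near 5%. Power differences were within simulation noise except at 1.5.

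A separate run used 150 subjects, dispersion 1.0, age SD 14, a cut at 50, a treatment rate ratio of 0.57 and 1,500 trials per setting. It gave −1.4%, −2.7% and −6.2% at 1.2, 1.3 and 1.5. Rejection rates were 0.781 v 0.789, 0.773 v 0.787 and 0.759 v 0.779 (stratum only v stratum plus years), each with a Monte Carlo error of about 1.1 points. The ratio 0.57 is weaker than the planning ratio of 0.6/1.4 = 0.43, so this run shows power differences more readily than the planned design would.

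**The case against.** The strongest reply is that nothing here is wrong. Adjusting for a factor as it was stratified is standard and keeps the type I error. Stratified randomisation already balances age. The count and logistic models adjust for the baseline lesion count, which protocol 6.1.2 itself ties to age. The imputation model also uses counts at earlier post-baseline visits. No document gives an age effect, a cut-point or the number of age categories. A linear term adds an assumption, and SAP 3.2 already foresees dropping region if the imputation model fails.

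Most of this stands, and it is why the point is optional. It does not remove the gain: the simulation in step 4 includes a baseline count correlated with age and still finds a reduction. The stratum stays in the model, so the linear term only has to capture some of the gradient within strata.

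A reader might infer more than the documents support:

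- **That every efficacy model is shown to use strata.** It is explicit in two places and inferred elsewhere.
- **That age drives new tumours.** The protocol reports a correlation.
- **That 64% of the information in age is kept.** That figure belongs to a median split of a normal variable; it is not known for this trial, and more than two levels would lose less.
- **That the aBCCdex ANCOVA is deficient.** It adjusts for its own baseline score, and no passage says that age predicts this patient-reported outcome.

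**Conclusion.** The point holds as a minor refinement. The planned analysis is valid and unbiased, and its sample size reproduces. With a two-level stratum and an age effect of 1.2 to 1.3 per decade, both assumed, the variance of the log rate ratio would fall by roughly 1 to 3%. That is about 1 to 4 of 126 subjects (126 × 0.01 = 1.3; 126 × 0.03 = 3.8). The reduction reaches about 8% only at 1.5 per decade, which is a steep gradient: 1.5⁴ = 5.1-fold over 40 years. If age has no effect, the cost is about 0.4%. A reader might take this as a loss of power that threatens the trial; the calculations show little or no visible change.

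**What to change.** Before unblinding, add age in years at consent as a linear covariate beside the age stratum in:

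- the negative binomial models for new BCCs and nSEBs and the logistic models for the proportions with new lesions (protocol 12.6.2; SAP 2.5.1 and 2.5.2);
- the imputation model for these counts (protocol 12.7.6; SAP 3.2).

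Keep the stratum for randomisation and subgroups. Leave the aBCCdex ANCOVA unchanged. State how age is set for subjects with only a year of birth on record, and whether the linear term is dropped before or after region if the imputation model fails.

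The cost is wording in two documents and one degree of freedom per model; no new data are needed. The SAP sections have to be revised in any case, because the SAP of 17 June 2020 still names nSEBs as the primary endpoint while protocol 12.6.1.1 names new BCCs.
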